3.3 Participants

Healthy, sedentary (not exercising regularly for the past 6 months), older adult males (N=30; Post-ex n=9, Pre-sleep n=11, Ex only n=10) between the ages of 60-75 years old from the Tallahassee area participated in the study. Health-related exclusion criteria included diagnosis of cardiac or peripheral vascular disease, stroke, kidney dysfunction, metabolic diseases, uncontrolled hypertension, orthopedic limitations, skeletal muscle complications, milk allergy, psychiatric conditions, use of psychotropic drugs or cognitive impairment. Additional exclusion criteria included participation in a structured regular exercise program within the past 6 months, actively attempting to increase or decrease body mass, scoring 26 points or less on the Montreal Cognitive Assessment, and/or body mass index (BMI) of ≥ 35 kg/m². To determine exclusion criteria, all participants completed an informed consent (appendix C), health history questionnaire (appendix E), physical activity questionnaire (appendix F), Montreal Cognitive Assessment (appendix G), and height and weight measurements, prior to any participation in the intervention. Lastly, all participants submitted a physician consent (appendix D) form prior to beginning the exercise training protocol.

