3.8 Sample Size Justification and Statistical Analysis

An a priori analysis was conducted with an effect size F of 0.25 calculated using mean and standard deviations from previously reported changes in LBM in older men (350) with power set to 0.8 and α set to 0.05 for 3 groups and 3 measurements. With an expected dropout rate of 15% (110), a sample size of 36 was adequate and provided an even distribution between groups.

A one-way analysis of variance (ANOVA) was used to analyze baseline differences and total training volume among groups. A 3x2 mixed model ANOVA with group as the between subjects' factor (Post-ex, Pre-sleep, Ex only) and time as the within-subjects factor (pre and post) was performed on all dependent variables except for muscle thickness, 1-RM strength, muscle power, and appetite, where a 3x3 mixed model ANOVA (Post-ex, Pre-sleep, Ex only x pre, mid, post) was used. Pearson product-moment correlation, or Spearman's correlation in the event of normality violation, was used to determine the relationship between changes in free IGF-1 and changes in body composition, muscle thickness, 1-RM strength, muscular power, and cognitive assessments.

Outliers were removed and defined as values outside of the mean \pm 3 standard deviations. Data were tested for normality (Shapiro-Wilk), homogeneity of variances (Levene's test), and sphericity (Mauchly's test) where appropriate. When normality or homogeneity of variances was violated, non-parametric testing or data transformation was performed. For a mixed model ANOVA, if transformation could not correct the violation, original data were analyzed, as there are no non-parametric alternatives. When sphericity was violated, the main time and group x time interactions were interpreted with the Greenhouse-Geisser estimation.

Significance was set at $p \leq 0.05$. Trends were noted for p -values between 0.051-0.10. For significant interactions and main effects, pairwise comparisons with Bonferroni adjustments were conducted (296, 332). Pearson correlation coefficients (r) or Spearman's correlation coefficients (r_s) were interpreted as "negligible" = < 0.30 , "low" = $0.30-0.50$, "moderate" = $0.50-0.70$, "high" = $0.70-0.90$, and "very high" = > 0.90 (244). Percentage change was calculated as $((\text{post value} - \text{pre value}) * 100)$. All analyses were performed with SPSS version 25

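### The ±3 SD removal rule has no error check, keep-all analysis or stated reference set: by arm and visit it flags almost nothing; pooled on the raw scale it often deletes valid skewed values

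*Combined protocol and SAP*

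**What the plan says.** The rule is one sentence in Section 3.8: "Outliers were removed and defined as values outside of the mean \pm 3 standard deviations". Nothing in the section says whether the mean and SD are taken within arm, within visit, over all men, on change scores or on model residuals. No check that a flagged value is a mistake is required, and no analysis with flagged values retained is planned.

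The following sentences of Section 3.8 cover assumption checks: "When normality or homogeneity of variances was violated, non-parametric testing or data transformation was performed". For the mixed ANOVA, "if transformation could not correct the violation, original data were analyzed, as there are no non-parametric alternatives". The order of outlier removal and these steps is not given, nor whether removed values return when the analysis falls back on untransformed data.

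Section 3.3 gives the sample: "N=30; Post-ex n=9, Pre-sleep n=11, Ex only n=10". Section 3.7.7 shows that the plan can define a quality-based exclusion: IGF-1 results needed an intra-assay CV below 15%.

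**The concern.** A rule based on distance alone does not separate a wrong value from a true but unusual one. How it behaves depends on how many values supply the mean and SD, and that is what the plan leaves open.

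In very small sets an extreme value inflates its own SD so much that it cannot reach 3 SD. In larger sets the rule can act, but on a right-skewed outcome it will tend to remove the upper tail, which is part of the distribution.

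The arms hold about ten men each. In the usual repeated-measures ANOVA, one deleted visit drops the man from that outcome: 1/9 = 11%, 1/10 = 10% or 1/11 = 9% of an arm. A reader of the results could not tell whether the rule had been almost idle or had removed genuine responses.

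**Working it through.** **Inputs.** The 3 SD threshold is from Section 3.8 and the arm sizes 9, 11 and 10 (total 30) are from Section 3.3. Distribution shapes and the pre/post correlation are assumptions, because the documents contain no outcome data. The only design figure in Section 3.8 is the sample size of 36. It can be reached under an assumed correlation of 0.5 (within-factor test: 28, or 30 with equal arms; 30/0.85 = 35.3, rounded up to 36). This point does not depend on it.

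**Step 1: the largest z a sample allows.** The extreme case is n−1 equal values and one value at distance d from them. The mean shifts by d/n, the outlying value deviates by d(n−1)/n, and the SD (n−1 divisor) is d/√n. The largest possible z is therefore (n−1)/√n.

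| Values in the reference set | (n−1)/√n | With n-divisor SD, √(n−1) |
|---|---|---|
| 9 (Post-ex) | 8/3 = 2.667 | 2.828 |
| 10 (Ex only) | 9/√10 = 2.846 | 3.000 (not outside 3) |
| 11 (Pre-sleep) | 10/√11 = 3.015 | 3.162 |
| 30 (all men) | 29/√30 = 5.295 | 5.385 |

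Within arms at one visit, or on change scores within arms, nothing can be removed from Post-ex or Ex only under either SD. In Pre-sleep, removal needs ten nearly identical men and one extreme man; the simulated chance was 0 to 0.5%. The bound depends on the number of values in the set. Stacking two visits within an arm of 9 gives 17/√18 = 4.01, and the rule could then act.

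**Step 2: all 30 men at one visit, raw scale, every value valid.** Chance of at least one deletion, by simulation (40,000 to 100,000 samples per shape):

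| Assumed shape | Chance |
|---|---|
| Normal | 3.3% |
| Lognormal, log-SD 0.3 | 19% |
| Gamma, shape 2 | 31.5% |
| Lognormal, log-SD 0.5 | 38% |
| Exponential | 47% |
| Lognormal, log-SD 1.0 | 72% |

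**Step 3: effect on inference.** These simulations used the pooled per-visit rule with an assumed pre/post correlation of 0.7. With arms of 9, 11 and 10, two visits and the whole man dropped (8,000 runs), Type I error for group × time and the share of datasets losing at least one man were:

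| Assumed shape | Type I error, all kept | Type I error, after deletion | Datasets losing a man |
|---|---|---|---|
| Normal | 5.1% | 5.1% | not reported |
| Log-SD 0.3 | 4.9% | 5.1% | 33% |
| Log-SD 0.5 | 4.3% | 4.6% | 59% |
| Log-SD 1.0 | 3.6% | 4.2% | 91% |

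A separate simulation shifted one arm, so that a true effect existed:

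| Log-SD | Shrinkage of estimated effect | Significance call changed |
|---|---|---|
| 0.3 | about 4% | about 4% of datasets |
| 0.5 | about 10% | about 9% |
| 1.0 | about 29% | about 20% |

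**The case against.** The strongest defence is that the rule is mechanical, takes no account of arm, and does little harm. Type I error stays near or below 5%. For one assumed effect, power with all values kept against deletion was 62% and 62% (normal), then 65% and 63%, 62% and 61%, and 41% and 47% at log-SD 0.3, 0.5 and 1.0. A pooled rule can also catch real faults, such as an incomplete 24-hour urine collection or a watch that was not worn. Transformation and non-parametric tests are already planned. All of this stands, and it rules out any claim of inflated false positives. It does not address the shrinkage of a true difference, which error rates and power do not show.

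Some stronger readings are tempting but unsupported:

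- A reader might infer that valid results were in fact deleted. The documents report no removed value and no outcome distribution. The skewed shapes are assumptions, and log-SD 1.0 is an extreme one. Total mood disturbance, a difference of sums plus 100, is not naturally lognormal.
- A reader might infer that removal came before normality testing, because it is described first. Section 3.8 states no sequence. If screening followed a successful transformation, the deletion rate would return to about 3% per visit.
- A reader might say that the rule is wholly inert within arms. At n=11 it is nearly so, not entirely.
- A reader might say that it either does nothing or removes genuine results. A pooled rule can also remove errors.

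**Conclusion.** The concern holds in a limited form. That the plan removes values on distance alone, without an error check, a keep-all analysis, a reference set or an order of steps, can be read directly from Section 3.8. The within-arm, single-visit result is exact algebra and needs no assumption about the data.

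The pooled result is conditional. It applies if all 30 men form the reference set, the raw scale is used and the outcome is right-skewed. Under the assumed lognormal shapes, 19% to 72% of samples then lose a valid value per outcome and visit, against about 3% for normal data. A true difference is understated by about 4% to 29%. Both ranges depend on the assumed skew, and the second also on the assumed correlation of 0.7.

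The point should be corrected, since it can touch every outcome in arms of about ten men. It does not invalidate the design, and nothing here shows that a reported result is wrong.

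**What to change.** 1. Keep all values in the main analysis. Exclude a value only for a documented measurement or recording error, decided without knowledge of arm.
2. Assess normality and apply the transformation or non-parametric test that Section 3.8 already provides before any outlier screen.
3. Report the ±3 SD exclusion only as a sensitivity analysis on a stated reference set, for example pooled model residuals on the analysis scale. A within-arm set at one visit would leave this analysis empty for two of the three arms.
4. List each excluded value with its outcome, visit and arm.

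The cost is a few sentences in Section 3.8 and a rerun on data already collected. The downside is that a true extreme value stays in the main analysis and may widen an interval.

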Interpretation of the SPPB outcomes was in accordance with previously established values (140). Briefly, each SPPB test was scored on a 0-4 scale, based upon time or completion of the task, with lower values indicating worse performance and vice versa. Scoring for the balance portion of the SPPB will consisted of: 1 point for maintaining the side-by-side position for 10 seconds, 1 point for maintaining the semi-tandem for 10 seconds, and 1 point for maintaining the full-tandem position between 3–9.99 seconds or 2 points for maintaining the full-tandem position for 10 seconds. If the participant could not maintain the side-by-side position for 10 seconds, the balance portion was scored 0. The gait speed test scoring was based upon the amount of time to walk 4 meters at a normal pace using the following cut off times: 1 point for times greater than 8.70 seconds, 2 points for times between 6.21–8.69 seconds, 3 points for times between 4.82–6.20 seconds, and 4 points for times less than 4.82 seconds. If the participants could not complete the 4-meter walk, then the gait speed test was scored as 0. Lastly, the 5-chair stand scoring was also based upon cut off times including: 1 point for times greater than 16.70 seconds, 2 points for times between 13.70–16.69 seconds, 3 points for times between 11.20–13.69 seconds, and 4 points for times less than 11.19 seconds. If the participant could not complete a sit-to-stand task, then the 5-chair stand test was scored as 0. Once all portions of the SPPB were completed the scores from all 3 tests were summed together for a total score, with 12 being the highest possible score.

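### Section 3.8 keeps the ordinary mixed ANOVA after transformation fails for a reason that is wrong, and names no check analysis

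*Combined protocol and SAP*

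**What the plan says.** Section 3.8 makes the mixed ANOVA the test for every outcome. A 3x2 model with "time as the within-subjects factor (pre and post) was performed on all dependent variables" is the default. Strength, power, muscle thickness and appetite instead get a 3x3 model with a mid visit.

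The same section describes the checks: "Data were tested for normality (Shapiro-Wilk), homogeneity of variances (Levene's test), and sphericity (Mauchly's test) where appropriate". The general remedy is "When normality or homogeneity of variances was violated, non-parametric testing or data transformation was performed". The mixed ANOVA is then made an exception: "if transformation could not correct the violation, original data were analyzed, as there are no non-parametric alternatives". Sphericity failures have their own remedy (Greenhouse-Geisser), so the exception concerns normality and homogeneity of variances only. Extreme values are dealt with separately: "Outliers were removed and defined as values outside of the mean" plus or minus 3 SD.

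Section 3.3 gives the arms: "N=30; Post-ex n=9, Pre-sleep n=11, Ex only n=10".

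**The concern.** The fallback rests on a statement about methods that is not true, and it denies the mixed ANOVA a remedy that the preceding sentence of the plan allows in general. Because the mixed ANOVA is the test for all dependent variables, the rule reaches all three specific aims. For an outcome that fails a check and is not repaired by transformation, the plan names no rank-based, permutation or unequal-variance analysis to set beside the ANOVA, and does not commit to saying which outcomes were handled this way.

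Two things are at stake. Under skewed or heavy-tailed changes the ANOVA can lose power, so a real effect of protein timing could be missed in arms this small. Under large variance differences between arms its type I error can exceed 5%. In either case a reader cannot tell whether a conclusion depends on the fallback.

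**Working it through.** The plan gives no figure of its own on this point. The check has two parts: whether alternatives exist, and what difference they could make.

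**1. Alternatives exist.** For participant *i* in arm *g*, let D = post − pre. With two visits the participant effect cancels in D, and in the mixed ANOVA

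- interaction sum of squares = ½ Σ n_g (D̄_g − D̄)², on 3 − 1 = 2 df;
- error sum of squares = ½ ΣΣ (D_gi − D̄_g)², on 30 − 3 = 27 df.

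The factor ½ cancels in the ratio, leaving the one-way ANOVA F on D. On one simulated dataset with arms 9/11/10, both routes give F = 0.7481, p = 0.4828. Any three-group test on D therefore addresses group-by-time: Kruskal-Wallis or permutation for non-normality, Welch's ANOVA (a parametric remedy) for unequal variances. With three visits, permuting arm labels or using aligned ranks tests the 3x3 interaction.

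**2. Inputs for size.** Arm sizes come from section 3.3 and alpha 0.05 from section 3.8. The documents give no distributions, so every distribution below is an assumption.

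**3. Power, pre/post outcomes.** 1-SD shift in the n=11 arm, ANOVA / Kruskal-Wallis on change, all datasets:

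| Change distribution | No outlier removal | Repeat run, no removal | After 3 SD removal |
|---|---|---|---|
| Lognormal, log-SD 0.5 (mild skew) | 0.639 / 0.745 | 0.64 / 0.75 | 0.673 / 0.744 |
| Lognormal, log-SD 1 (strong skew) | 0.746 / 0.959 | 0.74 / 0.96 | 0.877 / 0.965 |
| t, 3 df | 0.707 / 0.808 | 0.70 / 0.80 | 0.761 / 0.811 |
| Normal | 0.595 / 0.560 | 0.60 / 0.55 | 0.592 / 0.557 |

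The last column assumes that removal is pooled over arms and acts on changes; section 3.8 does not say. Under that assumption the non-normal gaps shrink from 10–21 points (0.808 − 0.707 = 0.101; 0.959 − 0.746 = 0.213) to 5–9 points (0.811 − 0.761 = 0.050; 0.965 − 0.877 = 0.088).

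**4. Type I error.** All datasets, 6,000 runs each, ANOVA / Kruskal-Wallis / Welch on change:

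| Scenario, no true effect | ANOVA | Kruskal-Wallis | Welch |
|---|---|---|---|
| Normal, equal SD | 0.044 | 0.042 | 0.042 |
| Lognormal change | 0.032 | 0.046 | 0.038 |
| t, 3 df | 0.041 | 0.049 | 0.038 |
| n=9 arm has 2 times the SD | 0.079 | 0.057 | 0.050 |
| n=9 arm has 3 times the SD | 0.095 | 0.066 | 0.047 |
| n=11 arm has 3 times the SD | 0.063 | 0.060 | 0.051 |

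The Monte Carlo standard error near 0.05 is √(0.05 × 0.95 / 6,000) ≈ 0.003. A large SD in the n=10 arm falls between the n=9 and n=11 cases.

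**5. A capped score.** The SPPB components are "summed together for a total score, with 12 being the highest possible score". In one SPPB-like scenario (latent mean 11.3, SD 1, rounded, capped at 12), datasets that stayed non-normal gave power 0.458 for ANOVA and 0.429 for Kruskal-Wallis. That is no gain, and the direction is the same when all datasets are counted.

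**6. What cannot be sized.** How often an outcome reaches the fallback depends on whether the checks are run on visit values or on changes, and section 3.8 says only that data were tested. With strongly skewed changes, Shapiro-Wilk flags about 95% of datasets if run on changes but about 10% if run on visit values. With the n=9 arm at 2 and 3 times the SD, Levene's test rejects in 48% and 83% of datasets on changes but 12% and 18% on visit values (assuming a pre SD three times the change SD). So neither a fallback rate nor a power figure conditional on reaching the fallback can be relied on.

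**The case against.** The strongest reply is that little harm is shown. No document says that any outcome failed a check after transformation. The ANOVA holds its level under non-normality alone, and unequal variances matter only when they are large and fall in the wrong arm. SPPB, the obvious candidate for a failed normality check, gains nothing from ranks. All of this stands.

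A reader might go further and infer that the reported group-by-time tests are invalid, that non-normality inflated false positives, or that most outcomes passed through the fallback. The documents support none of these. Type I error under skewed or heavy-tailed change was 0.032 and 0.041, and the number of outcomes affected cannot be recovered from the text. If skew is multiplicative, transformation repairs nearly all failures: in one such set of scenarios only about 2–3% of datasets remained.

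It is also fair that the alternatives are partial. They address group-by-time, not the main effects or the Bonferroni pairwise comparisons. A permutation or aligned-rank test does not cure unequal variances. A Welch test used only after Levene rejects is itself a two-stage procedure. Finally, section 3.8 is written in the past tense with final arm sizes, so an added test could not be presented as pre-specified.

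These limits shape the remedy. They do not rescue the stated reason, and nothing elsewhere in the document supplies the missing check analysis.

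**Conclusion.** The point holds in a limited form. The reason given for the fallback is wrong, which follows from algebra and needs no assumption for pre/post outcomes, and no check analysis is named. The effect on this trial is unknown and probably modest.

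In assumed scenarios at 9/11/10 with a 1-SD shift in one arm and no outlier removal, Kruskal-Wallis on change has more power than ANOVA: about 0.75 against 0.64 under mild skew, 0.96 against 0.74 under strong skew, and 0.80 against 0.70 for t with 3 df. The advantage is smaller if outlier removal acts on changes. Kruskal-Wallis is slightly worse for normal changes and gives no gain for an SPPB-like score. ANOVA type I error is about 8 to 9.5% over all datasets when the smallest arm has 2 to 3 times the SD of the others. The finding is about an unjustified rule and a gap in reporting; it is not evidence that any particular conclusion is wrong.

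**What to change.** 1. Delete the clause saying that no non-parametric alternative exists.
2. State whether the normality and variance checks are run on visit values or on changes.
3. For each outcome that still fails a check after transformation, keep the mixed ANOVA and report beside it a sensitivity analysis of group-by-time, labelled post hoc if the data have already been analysed. Use the same fixed rule for all such outcomes:
   - pre/post, normality fails: Kruskal-Wallis on change;
   - pre/post, variances differ: Welch's ANOVA on change (both tests if both checks fail);
   - three visits: a permutation test of the 3x3 interaction, with its statistic stated once and a note that it does not cure unequal variances.
4. List the outcomes that took this route and flag any conclusion that differs between the two analyses.

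The cost is some wording and a few extra runs on data already collected. If the assumptions in fact hold, the companion test has about 3–4 points less power (Kruskal-Wallis 0.560 against 0.595; Welch 0.571 against 0.602). When variances are equal, Levene's test still rejects in about 6% of datasets (run on changes), and Welch in those datasets runs at about 7–8%. That is why it is reported beside the ANOVA and does not replace it.

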3.1 Overview of Experimental Design

The overarching aim of this project was to compare the traditional recommendation of immediate post-exercise protein consumption with nighttime pre-sleep protein intake during 12 weeks of resistance training on functional and cognitive adaptations in older adults. To achieve this, our design contained three groups who performed the same 12-week RET program two times per week and: 1) Consumed protein immediately post-exercise (Post-ex), 2) Consumed protein 30 minutes prior to sleep (Pre-sleep), or 3) Did not consume additional protein – exercise only (Ex only). Baseline total kilocalories (kcal) and protein intake were monitored to ensure no significant differences among groups occurred. The dependent variables consisted of pre- to post-intervention changes in body composition (i.e. lean mass, fat mass, and percent body fat), functional capacity (i.e. SPPB), nitrogen balance, free plasma insulin-like growth factor 1 (IGF-1), profile of mood states, and sleep evaluation, and digit symbol substitution and pattern comparison. Pre-, mid-, and post-intervention 1-RM, muscular power, and muscle thickness were assessed to determine the time course of muscular adaptations and appetite changes.

The pre-intervention measures took place over 2-3 days. All participants were instructed to refrain from vigorous physical activity at least 48 hours prior to all pre-testing measurements. On day 1, participants reported to the laboratory in the morning following an overnight fast (participants were encouraged to consume normal water intake) to complete the informed consent process, health history, and physical activity questionnaires. Thereafter, participants completed pre-training assessments including height and weight, baseline blood pressure, psychological and cognitive assessments, blood draw (IGF-1), body composition (DXA or BIA),

muscle thickness, muscular power, and the SPPB. Following the completion of day 1 assessments, participants were provided a 3-day food record, actigraphy watch, and 24-hour urine collection jug (nitrogen balance) to return prior to beginning the RET portion of the study.

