3.5 Protein Supplementation

Protein and placebo supplementation were provided in a double-blind, placebo-controlled manner throughout the 12-week intervention. Participants were randomly assigned (<https://www.randomizer.org>) to 1 of 3 groups: 1) Post-ex consumed a protein supplement immediately post-exercise and a non-caloric placebo 30 minutes before sleep, 2) Pre-sleep consumed a non-caloric placebo immediately post-exercise and the protein supplement 30 minutes prior to sleep, or 3) Ex only did not consume protein or placebo supplementation. Participants were instructed to fast for at least 2 hours prior to each exercise session and for 2 hours post exercise (9), except for the consumption of the protein or placebo supplement, along with a 190-kcal snack bar (Nature Valley™, Oats 'N Honey, General Mills, MN), to reduce the timing effects of normal meals on exercise adaptations. Additional instructions were given to consume the nighttime pre-sleep protein or placebo supplement at least 2 hours after their last feeding (e.g. meal or snack) and approximately 30 minutes before sleep with no other food. On non-exercise days, participants were instructed to consume the protein or placebo supplement in between their normal breakfast and lunch.

To ensure a double-blind, placebo-controlled design, an assistant not associated with outcome measures created containers of protein and placebo supplements in advance and did not reveal the identity until the conclusion of the study. Participants were provided two containers with approximately 25 servings (3.5 weeks of supplements) of protein and placebo

supplementations. Each serving was weighed on a digital scale (Etekcity Co., Anaheim, CA) and placed within individual sealable bags (Ziploc; SC Johnson Co., Racine, WI) to ensure accurate servings. Furthermore, both supplements were masked for flavor, and texture. Lastly, participants were instructed to mix their supplement only with water.

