3.7 Measurements of Dependent Variables

3.7.1 Anthropometrics, Blood Pressure, and Body Composition

Anthropometric and body composition measures took place at pre- and post-intervention points. Anthropometric measures of body mass (BM) (kg) and height (cm) were measured by a digital scale and stadiometer (SECA, Hamburg, Germany), respectively. Blood pressure was measured at baseline and the taper session of week 12 using an automated blood pressure machine (Omron, HEM-907XL, Vernon Hills, IL) after participants were seated, with their feet flat and arms rested at heart level for 5 minutes. Body composition was assessed via DXA (iDXA Lunar, GE, Madison, WI) by a trained technician. DXA is a commonly utilized, non-invasive assessment that uses x-ray to scan the body while in the supine position, which takes approximately 5-7 minutes. After completion of the body scan, the DXA system software determines the differences in attenuation of x-rays of two different energies among bone mineral content and soft tissue (lean and fat mass), from which body composition components fat mass, lean mass, and percent body fat can be calculated using machine specific algorithms (360). Unfortunately, due to a change in IRB regulations, after completing 8 DXA scans, we were no longer able to use that machine, and therefore, we measured body composition with a BIA machine (BIA 310e, Biodynamics Corp., Shoreline, WA). BIA is a commonly used, non-invasive method that uses a small test current (800 μ A at 50 kHz) to assess impedance, which is used to estimate body fat percentage. For the assessment, participants were asked to lie in a supine position, while two pairs of electrocardiography electrode tabs were placed on the right ankle and wrist. Thereafter, the test current was applied, and body composition was computed within the BIA machine. Test-rest reliability measured by intraclass correlation coefficients (model 3,1) for the body composition variables were: percent body fat, 0.969 (95% confidence

intervals: 0.753, 0.997); lean mass 0.994 (95% confidence intervals: 0.949, 0.999); fat mass 0.978 (95% confidence intervals: 0.826, 0.998).

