(IBM Corp., Armonk, NY) and GraphPad Prism version 8.1.1 (GraphPad software, San Diego, CA). Data are presented as mean values \pm standard deviation, unless otherwise stated.

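### The Post-ex versus Pre-sleep comparison, the trial's stated overarching aim, may end without a confidence interval because pairwise comparisons are tied to significant three-arm results; separately, the appetite schedule conflicts between sections.

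*Combined protocol and SAP*

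**What the plan says.** **Aim.** Section 3.1 states that the project set out to "compare the traditional recommendation of immediate post-exercise protein consumption with nighttime pre-sleep protein intake". That is a comparison of two of the three arms.

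**Analysis.** Section 3.8 fits a 3x2 mixed ANOVA, with "time as the within-subjects factor (pre and post) was performed on all dependent variables" apart from muscle thickness, 1-RM strength, power and appetite, which get a 3x3 model over pre, mid and post. The follow-up rule is "For significant interactions and main effects, pairwise comparisons with Bonferroni adjustments were conducted". Baseline differences are tested by one-way ANOVA, but no baseline covariate is named in the outcome models.

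**Reporting.** The end of section 3.8 says "Data are presented as mean values" with standard deviations, unless otherwise stated. Confidence intervals appear only for the reliability coefficients in sections 3.7.1 and 3.7.2.

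**Numbers and allocation.** Section 3.3 gives "N=30; Post-ex n=9, Pre-sleep n=11, Ex only n=10". Section 3.5 says "Participants were randomly assigned".

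**Appetite.** Section 3.8 places it in the pre/mid/post model, and the section 3.1 overview appears to link it to that time course. Section 3.7.5.1 describes ratings at pre- and post-testing. The week-6 list at the end of section 3.1 names strength, power and muscle thickness, but not appetite.

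**The concern.** A significant time effect leads to comparisons between visits, not arms. Under the stated rule, only a significant interaction or group main effect leads to Post-ex versus Pre-sleep. If neither occurs, the plan commits to no test and no interval for the trial's own question. Readers can derive the difference in mean change from the group means. They cannot derive its uncertainty from visit-level SDs without the pre-post correlation, which the plan does not commit to reporting.

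With arms this small, a non-significant three-arm test cannot distinguish no timing difference from too few men. An interval shows which differences remain possible.

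The pairwise step is also undefined. Comparing changes and comparing post values are different tests and can give different answers. For appetite, a 3x3 model cannot be fitted if no mid rating exists.

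**Working it through.** **Inputs from the documents.** Arms of 9, 11 and 10; alpha 0.05; Bonferroni over three pairs (0.05/3); f = 0.25; power 0.80; 3 groups; 3 measurements; 15% dropout; N = 36.

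**Assumed, not in the documents.** Pre-post correlation rho of 0.5, 0.7, 0.9 or 0.95; two-sided pairwise tests; Gaussian data with equal SD at each visit; Ex only midway between the timing arms.

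**1. The plan's own figure.** The noncentrality is lambda = f² × N × m / (1 − rho), taken at rho = 0.5 with sphericity.
- Interaction, m = 3: 0.0625 × 36 × 3 / 0.5 = 13.5, giving power 0.823 at N = 36, before any dropout allowance.
- Time main effect, m = 3: N = 30 in equal groups (power 0.840), and 30/0.85 = 35.3, rounded up to 36.

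So 36 reproduces under two readings. Neither sizes Post-ex versus Pre-sleep. This is context only; the figure is not disputed.

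**2. Width of the interval.** With two visits, the 3x2 interaction test equals a one-way ANOVA on change.
- Standard error in change-score SDs: sqrt(1/9 + 1/11) = 0.449.
- 95% half-width with 27 df and the SD treated as known: 2.052 × 0.449 = 0.92. Averaged over the estimated SD in simulation: 0.91.
- Half-width at the Bonferroni level, on the known-SD basis: 1.15.

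**3. Cost of the gate.** At a true difference of 1.22 change-score SDs and level 0.05/3, simulated power (rho in the order above) is 0.572/0.572/0.574/0.567 with the gate and 0.576/0.575/0.577/0.571 without it. The cost is about 0.003.

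The value 1.22 is illustrative. At rho = 0.5, N = 30 and m = 2, lambda = 0.0625 × 30 × 2 / 0.5 = 7.5. With three arms of 10 and Ex only midway, lambda = 5d², so d = sqrt(1.5) = 1.22.

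**4. How often no between-group pairwise step follows** (3x2 model; neither interaction nor group main effect significant):

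| True Post-ex vs Pre-sleep difference | rho 0.5 | 0.7 | 0.9 | 0.95 |
|---|---|---|---|---|
| 1.22 change-score SDs | 27% | 31% | 34% | 35% |
| 0.8 change-score SDs | 60% | 63% | 65% | 65% |
| Raw difference held at its rho 0.5 value | 27% | 11% | 0% | 0% |

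The third row differs because the change-score SD is sqrt(2(1 − rho)) raw SDs. It shrinks from 1 at rho 0.5 to 0.45 at rho 0.9, so the same raw difference becomes 1.22/0.45 = 2.7 change-score SDs.

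**5. What the pairwise step compares.** At 1.22 change-score SDs, power after a significant interaction is 0.57 if changes are compared and 0.43/0.27/0.08/0.04 if post values are. With the raw difference held fixed, post-value power is about 0.44–0.58. The size of the gap depends on scale; the ambiguity does not.

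**6. Baseline adjustment.** Mean 95% half-width in change-score SDs is 0.91 as planned at every rho. With ANCOVA it is 0.81/0.86/0.91/0.92.

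**7. Multiplicity of added intervals.** With no true difference, an unadjusted 95% interval excludes zero in 5% of trials, against about 1.6–1.8% for the planned route. At 1.22 change-score SDs, about 17–18% of trials would show an interval excluding zero beside a non-significant planned result.

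**8. Appetite.** Two places point to three ratings (section 3.8 and apparently the section 3.1 overview). Two point to two ratings (section 3.7.5.1, and the omission from the week-6 list). The sections cannot all be right as written.

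**The case against.** *The plan says pairwise comparisons were made for significant effects; it forbids nothing else, and its wording leaves room for intervals.* This stands as far as it goes. The point is that none is promised, not that one is excluded.

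*The frequencies depend on the scale chosen for the effect.* This stands. The documents give neither rho nor the scale of f. If f = 0.25 applied directly to change scores, d = 0.25 × sqrt(6) = 0.61 and the gate would close more often than at 0.8. The frequencies are illustrations. The half-width in change-score SDs does not depend on the assumed effect.

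*Unadjusted intervals for every outcome are looser than the planned tests.* This stands, and the fix labels them accordingly.

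*Baseline adjustment is a preference.* Largely so. A reader might infer that omitting the covariate biases the result. The arms were randomised, so the change analysis is unbiased and only precision is at issue. The test-retest ICCs of 0.969–0.995 in sections 3.7.1 and 3.7.2 are not 12-week correlations. They do make a high rho plausible for body composition and muscle thickness, where ANCOVA would gain little.

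*Mixed devices undermine body composition.* Section 3.7.1 says "after completing 8 DXA scans, we were no longer able to use that machine". A reader might infer that some men changed device between visits. The text does not say so, and it gives no basis for sizing an effect.

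**Conclusion.** The concern holds as one of estimation and reporting. The plan names a two-arm question, ties its test to a three-arm result, leaves the pairwise quantity undefined and promises no interval. At a half-width of about 0.91 change-score SDs, a null result is compatible with large timing differences, and only an interval would show that. The half-width rests on the stated arm sizes and a common SD of change; the frequencies rest on assumed effects and correlations.

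Two stronger readings are not supported. One is that the gate makes the timing test materially weaker: its cost is about 0.003 of power. The other is that the planned ANOVA is invalid.

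The appetite conflict is a separate, plain inconsistency. The documents do not settle whether a mid rating was taken. The change should be made, but nothing here invalidates the planned tests.

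**What to change.** 1. **Timing contrast.** For each outcome, report the Post-ex minus Pre-sleep difference in pre-to-post change with its 95% interval, whatever the omnibus result. State that the pairwise step compares changes. Keep the Bonferroni level for significance claims. Label the intervals as unadjusted for multiplicity, or give Bonferroni-level intervals as well, and label them post hoc if added now. Cost: wording and a re-run on existing data, with no loss of power for the planned tests. Some intervals will exclude zero where the planned test is not significant, so the labels matter.

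2. **Appetite.** Reconcile sections 3.1, 3.7.5.1 and 3.8. Use the 3x2 model if no mid rating was collected. Cost: wording, and possibly one refit.

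3. **Baseline adjustment, as a cheap precision gain.** For outcomes other than body composition, show ANCOVA beside the planned analysis, labelled post hoc if adopted now. Expect a useful gain at rho of 0.5–0.7, none at 0.9 and a slight loss at 0.95. Cost: one degree of freedom and a linear-slope assumption, which is doubtful for the SPPB because its score is capped at 12.

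4. **Body composition.** Keep the change-score analysis, which cancels a constant device offset for men measured on one device at both visits. State how many men, if any, were measured on different devices. If any were, show the result with and without them.
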